11.4.4 Related to Corticosteroids

Corticosteroids can make the body retain water and salt, cause diabetes and acne, and worsen high blood pressure. In addition, they will probably increase your appetite and may cause insomnia or mood changes. Steroids can also cause stomach ulcers and soften bones, leading to osteoporosis. The more dangerous problems, like bone thinning, only occur with long-term use; the other side effects will stop when the medication is discontinued. A small number of cases of "aseptic necrosis" have been observed when steroids have been used in high doses for durations comparable to those we will use in this study. Aseptic necrosis is a thinning of the bone near the joints, which can lead to chronic pain, sometimes requiring joint replacement. Steroids also suppress the immune system and raise your susceptibility to infection; taking CsA and steroids together increases this risk still further. We will ask that you plan to stay in the hospital for the first two weeks of your therapy so that infections, if they occur, can be treated promptly.

11.4.5 Related to bone marrow aspirate and biopsy: No major risks are involved with bone marrow aspirate and biopsy. However, a small risk of infections, pain, bleeding, and hematoma formation at the site of the aspiration exists with the procedure.

11.4.6 Related to blood draws: No major risks are involved with blood draws. Minor complications including bleeding, pain, and hematoma formation at the site of blood draws, vasovagal reactions or infections may rarely occur.

11.4.7 Related to Cardiac Monitoring

EKG: An electrocardiogram (EKG) is a test that measures the electrical activity of the heartbeat. With each beat, an electrical impulse (or “wave”) travels through the heart. This wave causes the muscle to squeeze and pump blood from the heart. A technician will put patches (electrodes) on the chest, arms and legs. The electrodes are soft and don’t cause any discomfort when they’re put on or taken off by the

technician. The machine only records the EKG. It doesn't send electricity into the body. There's no pain or risk associated with having an electrocardiogram.

11.4.8 Related to Central Line Placement

A catheter may be placed in a large vein of the neck, chest, or arm using local anesthetic. Patients will sign a separate consent for the placement procedure. Only trained experienced staff will place the line in order to minimize these procedure related risks.

The risks from the procedure are low; they include bleeding, bruising, or infection at the site of insertion. Very rarely (less than 1% of the time), the line placement may nick a vein causing one lung to collapse during line insertion. If the lung collapses, a tube may have to be inserted into the chest and remain in place until the lung re-expands. Because of this risk, patients will have a chest x-ray following the procedure to make sure the line is in the correct place and that the lung is not collapsed. Once placed, the line will remain in place until drug administration is complete.

11.4.9 Related to Concomitant Medications

- **Pentamidine:** cough (31-47%), bronchospasm (10-23%), decreased appetite (53-72%), fatigue, metallic taste, shortness of breath, decreased appetite, dizziness, rash, nausea, pharyngitis, chest pain/congestion, night sweats, chills, vomiting.
- **Valacyclovir:** Nausea and/or vomiting, headache, dizziness, abdominal pain, dysmenorrhea, arthralgia, acute hypersensitivity reactions, elevations in liver enzyme laboratory values (e.g. AST). Renal failure and CNS symptoms have been reported in patients with renal impairment who received valacyclovir at greater than the recommended dose.

11.5 Risks in Relation to Benefit

For adult subjects: The benefits to the subjects could be reduction or even abolition of transfusion requirements and/or improvement of cytopenia, resulting in improved quality of life and also decreased morbidity and mortality from transfusion-associated viral agents, iron overload, and/or a susceptibility to infections. Potentially, treatment with other more toxic therapies could also be avoided or postponed.

The benefits of this study and the acquisition of bone marrow and blood samples important for the understanding of the pathophysiology of immune-mediated bone marrow failure states have been described in the previous paragraphs.

For pediatric subjects: The inclusion of children satisfies the criteria set forth in 45 Code of Federal Regulations 46, Subpart D: 46.405 as follows:

- (a) the risk is justified by the anticipated benefit to the subjects: We are offering pediatric subjects with a probably lethal hematological disease an alternative to symptomatic therapy.
- (b) the relation of the anticipated benefit to the risk is at least as favorable to the subjects as that presented by available alternative approaches. The benefits to the patients could be reduction or even abolition of transfusion requirements and/or improvement of low peripheral blood counts, resulting in improved quality of life and also decreased morbidity and mortality from transfusion-associated viral agents, iron overload, and/or a susceptibility to infections. Potentially, treatment with other more toxic therapies could also be avoided or postponed.

(c) adequate provisions are made for soliciting the assent of the children and permission of their parents or guardians, as set forth in 46.408.

11.6 Informed Consent Processes and Procedures

Note: Effective January 21, 2019, a witness to the signature of the written long form research consent at an NIH site (whether initially approved by an IRB before or after January 21, 2019) is no longer a requirement.

The investigational nature and research objectives of this trial, the procedures and treatments involved and their attendant risks and discomforts and benefits, and potential alternative therapies will be carefully explained to the patient during the initial clinic evaluation. The Principal Investigator, [name], or the Associate Investigators on this protocol delegated to obtain informed consents will lead this discussion and obtain the informed consent. The consent form will be signed in the presence of the investigator and a witness prior to commencement of the treatment plan. The treatment plan and risks will be discussed again and in detail during their hospital visit for treatment.

If the subject is a minor, the parent who signs the consent for the minor must be a legally recognized parent or guardian. Where deemed appropriate by the clinician, and the child's parent or guardian, the child will also be included in all discussions about the trial and a minor's assent will be obtained. The parent or guardian will sign on the designated line on the informed consent attesting to the fact that the child had given assent.

In cases where parents share joint legal custody in making medical decisions of their child (e.g. by a custody agreement or court order) both parents must give their parental permissions regardless of level of risk of the research. Exceptions may be made if one parent is deceased, becomes incompetent or is not reasonably available (e.g. in prison).

If the minor subject is a female of childbearing age, she will be informed about pregnancy testing and will be told that if her pregnancy test is positive, we will counsel her and help her tell her parents or we will tell her parents. If she does not agree she will be advised not to sign the assent.

If at any time during participation in the protocol, new information becomes available relating to risks, adverse events, or toxicities, this information will be provided orally or in writing to each enrolled or prospective patient. Documentation will be provided to the IRB and if necessary the informed consent amended to reflect relevant information.

When a pediatric subject reaches age 18, continued participation will require re-consenting of the now adult with the standard protocol consent document to ensure legally effective informed consent has been obtained. Should sample or data analysis continue following completion of active participation and the subject has reached 18 years of age, we will attempt to contact the subject using the last known contact information to obtain consent for continued use of data or samples collected during their prior visit. Given the length of time that may have transpired for some of the subjects since their last visit for this study, we request waiver of informed consent for those individuals who after good faith efforts to contact them, we are unable to contact.

Requirements for Waiver of Consent consistent with 45 CFR 46.116 (d), each of which must be addressed in relation to the protocol:

- (1) The research involves no more than minimal risk to the subjects;
 - a) Analysis of samples and data from this study involves no additional risks to subjects.
- (2) The waiver or alteration will not adversely affect the rights and welfare of the subjects;

- a) Samples and data will be kept in secure locations in the laboratory of [name]. Retention of samples or data does not affect the welfare of subjects.
- (3) The research could not practicably be carried out without the waiver or alteration; and
 - a) Considering the length of time between a minor's enrollment and their age of majority, it is possible that more than a few subjects may be lost to follow up. A significant reduction in the number of samples analyzed could impact the quality of the research.
- (4) Whenever appropriate, the subjects will be provided with additional pertinent information after participation.
 - a) We only plan to request a waiver of reconsent for those subjects who have been lost to follow-up.

Informed Consent of Non-English-Speaking Research Participants.

We anticipate the enrollment of non-English speaking research participants into our study. The IRB approved full consent document will be translated into that language in accordance with the Clinical MAS Policy M77-2. If there is an unexpected enrollment of a research participant for which there is no translated extant IRB approved consent document, the Principal Investigator and or those authorized to obtain informed consent will use the Short Form Oral Consent Process as described in MAS Policy M77-2, 45 CFR 46.117 (b) (2) and 21 CFR50.27 (b) (a). The summary that will be used is the English version of the extant IRB approved consent document.

Informed Consent for adult research participants unable to provide consent:

If there is an unexpected enrollment of a research participant unable to provide informed consent, the following justification and procedures per NIH HRPP SOP 14E will be used to enrolled participants in this protocol.

Justification for inclusion: This research provides the prospect of direct benefit; therefore, inclusion is justified. The benefits to the participants could be improvement of cytopenias resulting in improved quality of life and also decreased morbidity and mortality from transfusion-associated viral agents, iron overload, and/or a susceptibility to infections. Potentially, treatment with other more toxic therapies could also be avoided or postponed. Not allowing participants who cannot provide consent would deny them the potential benefits this protocol offers for their AA. There are no plans to include institutionalized participants.

Consent and Assent:

Procedures to determine capacity: If documentation of decision making capacity is not present in the medical record or the investigator questions the decision-making capacity of the individual, then the Ability to Consent Assessment Team (ACAT) [contact] or [contact]) will be contacted to make the determination.

Procedures for obtaining consent for legally authorized representative (LAR) (Category B per SOP 14E). See Appendix F for details.

11.7 Conflict of interest

The Principal Investigator assured that each associate investigator listed on the protocol title page received a copy of the NIH's Guide to preventing conflict of interest. Investigators added subsequent to the initial circulation were provided a copy of the document when they were added. Copies of the Conflict of Interest Statement were forwarded to the Clinical Director. No initial or subsequent members of the research team reported a potential conflict of interest.

This protocol has an associated CRADA with Novartis.

11.8 FWA Coverage Agreement

[name] is currently working at Medimmune and will be analyzing identifiable data as an Non-NIH, Non-Enrolling Engaged Investigator in this protocol. [name] role in the research will be limited to data analysis. An FWA coverage agreement to cover this activity has been executed by [name] and [name].

11.9 Collaboration(s)

[name]. will continue to collaborate on trial with protocol related questions and interpretation of study data. [name] has no access to PII and is no longer participating in direct patient care.

Between NHLBI ([name]) and [name]., Ph.D. Professor of Translational Hematology in University of Helsinki (Medicum) and Helsinki University Hospital. Upon execution of the MTA, de-identified (coded) peripheral blood and plasma samples of Severe Aplastic Anemia patients will be sent for sequencing of DNA using Next Generation Sequencing (NGS), analyze results, seeking somatic mutations in lymphoid cells, T-cell receptor (TCR) usage, and autoantibody identification by imputation. Collaborator will return the results of the analysis to NHLBI for further analysis and correlation of results with NHLBI's clinical data, especially clinical outcome. Both parties intend to jointly design experiments and analyze the results and data, and publish the results in co-authored articles.

Between NHLBI ([name].) and [name]., Ph.D. at Kings College London. Upon execution of the MTA, de-identified (coded) bone marrow samples of Severe Aplastic Anemia patients will be sent to investigate freshly stained bone marrow cells, HSPCs, and supporting cells (stromal cells, macrophages, myeloid-derived suppressor cells, and their inflammation cytokine production). Additionally, the samples collected after the treatment will be analyzed similarly to explore mechanisms by which eltrombopag stimulates hematopoiesis and modulates the immune system. Collaborator will return the results of the analysis to NHLBI for further analysis and correlation of results with NHLBI's clinical data.

12. PHARMACEUTICALS

12.1 ELTROMBOPAG (PROMACTA®)

Supply: The drug Novartis is providing for this study may be either investigational or commercial material, based on their supply, and is available in tablets and as a powder for oral suspension. Each sachet contains eltrombopag olamine equivalent to 25 mg of eltrombopag. The tablets are available as 12.5, 25, 50, and 75 mg tablets.

Preparation: There is no parental dose for eltrombopag.

Storage and Stability: Store at 25°C (77°F); excursions permitted to 15° to 30°C (59° to 86°F) [see USP Controlled Room Temperature].

Administration: Eltrombopag may only be given orally.

Toxicities: see section 11.4.3 Risks related to eltrombopag.

Tablets:

White, round, film-coated tablets without debossing are provided, containing eltrombopag olamine equivalent to 12.5 mg, 25 mg, 50 mg, or 75 mg of eltrombopag free acid. Tablets are packaged in white HDPE bottles with white plastic, induction-seal, child-resistant caps.

Commercial image actives (12.5 mg - white, 25 mg- orange or white, 50 mg blue or brown, 75 mg – pink,) which are equivalent to the clinical forms with the exception of the film coated color may also be provided for clinical use. These forms are also packed in white HDPE bottles with white plastic, induction -seal, child-resistant caps. Desiccant may be included. Additionally, the commercial image tablets may be provided in aluminum foil blister packages.

Eltrombopag Powder for Oral Suspension:

Eltrombopag powder for oral suspension (Eltrombopag PfOS) is a reddish-brown to yellow powder contained inside an elongated sachet. A 25 mg PfOS strength is available, containing eltrombopag olamine equivalent to 25 mg of eltrombopag free acid. The powder blend composition contains eltrombopag olamine equivalent to 20 mg of eltrombopag free acid. The powder fill weight is 1.25 gram for PfOS 25 mg.

PfOS sachets will be packaged in a carton. PfOS may be supplied as bulk stickpacks (sachets) or as commercial kit. If bulk stickpacks are supplied, the clinical site will also receive reconstitution bottle, syringe-adapta cap, and 20mL oral dosing syringes. If commercial kit is provided, each carton pack will hold 30 sachets along with a plastic reconstitution container, a syringe-adapt cap and 30 single-use 20mL oral dosing syringes. The sachet should not be opened until ready to use. Add 9.5 mL of water drawn using a 20mL syringe into the provided plastic container. Cut open the sachet and add the entire content of the sachet into the container with water. The container is capped and shaken for 10-20 seconds. The resulting suspension contains 2 mg/mL of eltrombopag dose. The prescribed volume (dose) is drawn through the syringe port on the cap with a syringe. Upon dosing, the rest of the remaining suspension in the container is discarded. The container and cap are rinsed with water and dried. If the prescribed dose is > 29 mg, which will require that part or all of a second sachet be used, then the suspension can be prepared by adding the contents of the two sachets to 19.0 mL of water, and then following the steps outlined above. The water has to be drawn by using the 20cc syringe, and similarly dosing has to occur by using the same 20cc syringe. If the dosage requires more than two sachets, then for each sachet used 9.5 mL of water will be added, and then following the steps outlined above. The water has to be drawn by using the same 20cc syringe for each sachet used, and similarly dosing has to occur by using the same 20cc syringe. A fresh dose is prepared everyday just prior to the dosing and no storage of the reconstituted suspension is allowed.

Handling and Storage of Study Treatment: Eltrombopag PfOS sachets will be stored at a controlled room temperature of 20-25°C (68-77°F); excursions between 15-30°C (59-86°F) are permissible.

Shipping: The NIH Investigational Drug Management and Research Section (IMDRS) will be responsible for receiving, storing, dispensing and accounting for drug product. The shipping address for Novartis supplied investigational agent is:

National Institutes of Health/CC/PHARM/IMDRS
[name]
[name]
Shipping Designee Name: [name]
Shipping Designee [contact]
Shipping Designee [contact]
Shipping Designee e-mail: [contact]

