5.3 Eltrombopag

Subjects will initiate eltrombopag at a starting daily dose as detailed in Table 3, according to age and ethnicity. Subjects between 12 and 17 years of age will receive the adult dose of 150 mg. Those between 6 and 11 will start at 75 mg, and children between 2 and 5 years of age will be started at 2.5 mg/kg (Table 3). To adjust for the higher expected exposure in children of East Asian and South East Asian ancestry, the starting dose for East Asian and South East Asian subjects between 12 and 17 years of age will be 75 mg once daily. For East Asian and South East Asian subjects between 6 and 11 years of age, the starting dose will be 37.5 mg once daily, and for children between 2 and 5, the starting dose will be 1.25 mg/kg (Table 3). Eltrombopag will be administered orally as tablets or an oral suspension from sachet of eltrombopag powder. Each 25 mg Pfos sachet contains eltrombopag olamine equivalent to 25 mg of eltrombopag free acid. If a child's dose is based on body weight and needs a dose of 28 mg, then dose only single sachet that provides 25 mg dose. However, if the child needs a dose of 29 mg or greater, then the suggestion is to start using the second sachet. This is mainly suggested to prevent the wastage of medicine by opening a second sachet to meet the additional 1-3 mg dose. Dosing 25 mg where a patient needs 28 mg should not have a significant impact on PD response. If an adult receives the oral suspension administration of eltrombopag, the required number of sachets will be used to administer the below adult doses.

Table 3. Dosing according to age and ethnicity

Age groups	Daily dose
Non-Asian	
12-85	150 mg
6-11	75 mg

Age groups	Daily dose
2-5	2.5 mg/kg
East Asian, South East Asian	
12-85	75 mg
6-11	37.5 mg
2-5	1.25 mg/kg

Eltrombopag may be taken on an empty stomach (1 hour before or 2 hours after a meal) or with food containing little (<50 mg) or preferably no calcium or dairy products. Allow at least a 4-hour interval between eltrombopag and other medications or products containing polyvalent cations (e.g. calcium, magnesium, aluminum, zinc, selenium or iron) such as antacids, dairy products, and mineral supplements to avoid significant (70-75%) reduction in eltrombopag absorption due to chelation.

Dose delay or dosing interruptions:

Cohort 1:

Eltrombopag dose may be interrupted when clinically indicated at the discretion of the investigator. Interruptions will be recorded in the medical record.

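### Section 12.1 is inconsistent on suspension strength: 25 mg in 9.5 mL of water is not 2 mg/mL, so part-sachet doses drawn by volume are probably up to 16–32% high

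*Combined protocol and SAP*

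**What the plan says.** Section 5.3 sets the sachet content: "Each 25 mg Pfos sachet contains eltrombopag olamine equivalent to 25 mg of eltrombopag free acid". Section 12.1 gives 25 mg twice more, under supply and again in the description of the powder.

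For preparation, Section 12.1 says: "Add 9.5 mL of water drawn using a 20mL syringe into the provided plastic container". The whole sachet goes in and the bottle is shaken. The strength is then given: "The resulting suspension contains 2 mg/mL of eltrombopag dose". Dosing is by volume: "The prescribed volume (dose) is drawn through the syringe port on the cap with a syringe". Whatever is left is discarded.

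Larger doses keep the same ratio. The two-sachet mix is made by "adding the contents of the two sachets to 19.0 mL of water". Beyond that: "If the dosage requires more than two sachets, then for each sachet used 9.5 mL of water will be added".

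Section 12.1 also carries a second content figure with no denominator: "The powder blend composition contains eltrombopag olamine equivalent to 20 mg of eltrombopag free acid". The next sentence reads: "The powder fill weight is 1.25 gram for PfOS 25 mg".

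**The concern.** The strength is what turns a prescribed dose in mg into a drawn volume, and 2 mg/mL is the only strength the protocol gives. If the bottle is stronger than stated, every dose that uses part of its contents is too large. A dose that uses the whole bottle is right whatever the strength, because the bottle simply runs out.

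Most exposed are children aged 2–5, dosed at 2.5 mg/kg or 1.25 mg/kg under Section 5.3, and any older patient on a part-sachet suspension dose. Two further uses depend on the figure. Section 5.4 cuts the dose by 12.5 mg in children under 12 when platelets exceed 200,000/µL, a rule that Section 2.7 ties to concern about thrombosis. Appendix D records the dose on the PK day in mg, so a suspension dose converted at 2 mg/mL could be recorded wrongly.

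**Working it through.** **Inputs from the documents.** Sachet content C = 25 mg (5.3; 12.1 twice), with 20 mg as the competing figure (12.1). Water is 9.5 mL per sachet (12.1). Stated strength is 2 mg/mL (12.1). Powder weight is 1.25 g per sachet (12.1). A second sachet is used from about 29 mg (5.3, 12.1).

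**Assumption.** The documents do not say how much volume the powder takes up. I use d = 0 to 1.25 mL per sachet, that is, up to 1 mL per gram.

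**Can the stated 2 mg/mL be reproduced?** Strength = C / (9.5 + d).

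- C = 25: 25/9.5 = 2.63 mg/mL at d = 0; 25/10.75 = 2.33 mg/mL at d = 1.25. Against 2 mg/mL this is +31.6% to +16.3%.
- To get 2 mg/mL from 25 mg, the final volume must be 25/2 = 12.5 mL. The powder would have to add 12.5 − 9.5 = 3.0 mL, or 3.0/1.25 = 2.4 mL per gram, which is implausible.
- C = 20: 20/9.5 = 2.11; 20/10.0 = 2.00; 20/10.75 = 1.86 mg/mL. The stated figure is reproduced, but only by contradicting the 25 mg content.

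**Which content is better supported?** 25 mg is stated three times. The 20 mg figure is reconciled with it if it means 20 mg per gram of blend: 20 × 1.25 = 25 mg. The words per gram are not printed, so this remains an inference.

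**Delivered dose.** With n sachets and prescribed dose D drawn at 2 mg/mL:

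delivered = n × C × min(1, (D/2) / (n × (9.5 + d)))

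| Prescribed, mg | n | Volume called for, mL | Volume in bottle, mL | Delivered if C = 25, mg | Delivered if C = 20, mg |
|---|---|---|---|---|---|
| 15 | 1 | 7.5 | 9.5–10.75 | 17.4–19.7 (+16 to +32%) | 14.0–15.8 (−7 to +5%) |
| 20 | 1 | 10.0 | 9.5–10.75 | 23.3–25.0 (+16 to +25%) | 18.6–20.0 (−7 to 0%) |
| 22.5 | 1 | 11.25 | 9.5–10.75 | 25.0 (+11%) | 20.0 (−11%) |
| 25 | 1 | 12.5 | 9.5–10.75 | 25.0 (0%) | 20.0 (−20%) |
| 30 | 2 | 15.0 | 19.0–21.5 | 34.9–39.5 (+16 to +32%) | 27.9–31.6 (−7 to +5%) |
| 37.5 | 2 | 18.75 | 19.0–21.5 | 43.6–49.3 (+16 to +32%) | 34.9–39.5 (−7 to +5%) |
| 62.5 | 3 | 31.25 | 28.5–32.25 | 72.7–75.0 (+16 to +20%) | 58.1–60.0 (−7 to −4%) |
| 75 | 3 | 37.5 | 28.5–32.25 | 75.0 (0%) | 60.0 (−20%) |

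The 15 mg and 30 mg rows are the limiting starting doses at 12 kg: 1.25 × 12 and 2.5 × 12.

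**First platelet reduction on suspension, 75 to 62.5 mg.** If C = 25, the real cut is 75 − (72.7 to 75.0) = 0 to 2.3 mg instead of 12.5 mg. The next step, to 50 mg, is two whole sachets and delivers 50 mg.

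**Reach.** Section 11.1 expects roughly 20% under 18: 207 × 0.20 ≈ 41. The documents do not give the number aged 2–5. If it were 10–25% of these (an assumption), that would be about 4–10 children. The number aged 6–11 and the share taking suspension are also not given.

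**The case against.** The strongest objection is that the direction is not settled. Section 12.1 prints both 25 mg and 20 mg, and 20 mg in about 10 mL matches the stated strength. A reader might infer that overdosing is established. It is not. That conclusion needs the sachet to hold 25 mg and volumes to have been worked out at 2 mg/mL, and the documents do not show what volumes were prescribed. The 32% end also requires 1.25 g of powder to occupy no volume.

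A reader might also infer that the platelet rule, and with it the protection against thrombosis, fails whichever content is right. The documents do not support that. At 20 mg per sachet, a child prescribed 75 mg already receives 60 mg, below the reduced target of 62.5 mg, so the small cut carries no excess exposure. On the 25 mg reading the loss is real but short-lived: Section 5.4 repeats reductions every 2 weeks, the 50 mg step is delivered correctly, and drug is stopped for a week above 400,000/µL.

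Two limits on reach also stand. The tablets listed in 12.1 (12.5, 25, 50 and 75 mg) can make up every fixed dose and every 12.5 mg step from it, so a patient who takes tablets is not exposed. PK sampling covers only Cohort 1 and Extension Cohort subjects from number 120. The mismatch may also show itself in use, since a 25 mg dose calls for 12.5 mL from a bottle holding about 10 mL.

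None of this removes the contradiction. No plausible displacement reconciles 25 mg, 9.5 mL and 2 mg/mL.

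**Conclusion.** The point holds as an internal inconsistency in Section 12.1, and that part is certain. On the better-supported 25 mg content, part-sachet suspension doses run high by up to 16–32%, given 0–1.25 mL of powder displacement. The excess shrinks to 11% at 22.5 mg and to nil at whole sachets. A first cut from 75 to 62.5 mg on suspension is nearly lost until the next step. If a sachet holds 20 mg, part-sachet doses that do not empty the bottle are within −7% to +5%, whole-sachet doses are 20% low, and there is no overdose or thrombosis concern.

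Few patients are likely to be affected. Sample size, power and the primary efficacy endpoint do not depend on the figure. It should still be corrected, because it is the only preparation instruction in the documents and it sets doses in young children.

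**What to change.** 1. Have the pharmacy confirm the content of a sachet and the final volume after mixing.
2. Correct 12.1 so that the one-, two- and multi-sachet instructions share one water volume and one strength. If content is 25 mg, either use 12.5 − (0 to 1.25) = 11.25–12.5 mL of water per sachet for a true 2 mg/mL, or keep 9.5 mL and state the measured strength. If content is 20 mg, correct the 25 mg statements in 5.3 and 12.1 instead.
3. Complete the 20 mg sentence with its denominator, or remove it.
4. Where drawn volumes were recorded, correct past suspension doses in the safety and PK summaries: part-sachet doses if content is 25 mg, whole-sachet doses as well if it is 20 mg. Otherwise state the possible error as a limitation. The documents do not say that volumes were recorded.

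The cost is one pharmacy check, a wording amendment and, where records allow, a limited correction of past doses. No patients or procedures are added.
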